### **Référence au spécialiste dans le cadre de la douleur thoracique :**

Aucune

Cardiologue  *Si oui*, nombre de consultation(s) : \_\_\_\_

Autre spécialiste  (préciser) : \_\_\_\_\_ nombre de consultation(s) : \_\_\_\_

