### 3.2 Endpoints

In order to assess implementation and effectiveness of the cardiovascular CPR (targeted at GPs) on the management of chest pain and patient's outcome, we will measure:

- Hospitalizations, severe CHD at 9 months among patients included
- Number and type of extra investigations and referrals run by GPs to manage patient's chest pain
- Use/non use of the CPR by GPs, acceptability and satisfaction

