## 6. Evaluation criteria

Aiming to assess both implementation of the cardiovascular CPR and its potential effect on chest pain management, evaluation criteria are split in two classes. On one hand, criteria concerning use of the CPR, evaluated by few questions in de CRF directly addressed to GPs. On the other hand, criteria aiming to measure impact of the CPR on chest pain management and patient's outcome. These are to be filled in by GPs for each patient complaining of chest pain at the time of the index visit (CRF) and at the end of follow-up (6 to 9 months), and by research team for intermediate analysis.

Implementation:	
Acceptability of the CPR	
 
- Use/non use of the CPR
 
- Reassurance with low-risk result
 

Satisfaction	
 
- Discrete visual analogue scale
 

Impact:	
Extra investigations of chest pain	
 
- None
 
- ECG
 
- Thoracic radiography
 
- Laboratory (CRP, FSC, CK, D-dimers, Troponines, BNP)
 
- Cardiac stress test
 
- Others (precise)
 

Referral	
 
- None
 
- Hospital / emergency setting
 
- Cardiologist (less than 6 hours, less than one week, more than one week, telephonic interview)
 
- New consultation
 
- Other (precise)
 

Patient's outcome at 9 months	
 
- Hospitalisation(s) during follow-up
 
- CHD / no CHD, with degree of certainty (discrete visual analogue scale)
 

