## 7. Data collection and management

### 7.1 Source data

- CRF filled in by GPs for each patient included at index visit (see Annex 2, in French)
- Intermediate analysis questionnaire (see Annex 3, in French)
- End of follow up questionnaire (see Annex 3, in French)

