**Suite de prise en charge :**

Aucune  Hôpital/Urgences

Consultation par cardiologue : délai <6 heures  <1 semaine  >1 semaine   
avis téléphonique

Consultation de contrôle au cabinet

Autre(s)  (préciser) : \_\_\_\_\_

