### **Suivi du patient :**

Le patient a-t-il été revu *en raison de la douleur thoracique* **APRES** la consultation initiale :  
 oui  / non

*Si oui*, nombre de consultations ultérieures en lien avec la douleur thoracique : \_\_\_\_

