### **Hospitalisations en lien avec la douleur thoracique durant la période de suivi :**

oui  / non

*Si oui*, durée : \_\_\_\_ jour(s)

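### The 3- and 9-month form has no hospital/emergency referral category, although Section 6 says that category is recorded at follow-up

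*Protocol*

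**What the plan says.** Section 3.2 makes referrals an endpoint: "Number and type of extra investigations and referrals run by GPs". Section 6 lists the Referral categories, one of which is "Hospital / emergency setting". It says the impact criteria are completed "at the time of the index visit (CRF) and at the end of follow-up (6 to 9 months), and by research team for intermediate analysis". Section 10.2 carries Referral as a row in the between-arm table (item f), and item e compares the endpoints between arms in low-risk patients.

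Section 7.1 names the source documents: the index CRF (Annex 2) and the questionnaires for the intermediate analysis and the end of follow-up (both Annex 3). The index CRF has a tick box "Hôpital/Urgences". Annex 3 is a single form, completed by a research nurse at 3 months and by the physician at 9 months. Its relevant items are:

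- "nombre de consultations ultérieures en lien avec la douleur thoracique", a total count;
- "Référence au spécialiste dans le cadre de la douleur thoracique", with none, cardiologist or other specialist (to be specified);
- "Hospitalisations en lien avec la douleur thoracique durant la période de suivi", yes or no, with days.

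**The concern.** A category that Section 6 assigns to follow-up is missing from the only form used at follow-up. The analysis compares referrals between arms, and the hoped-for effect of the score is fewer of them. Emergency referral is recorded cleanly on the day of the index visit and not cleanly afterwards. The comparison is therefore sensitive to when a referral happens as well as whether it happens. If a low score leads some GPs to wait and refer later, the index count falls and the later referral may go unrecorded.

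The 3-month look uses the same form and carries the stopping rule on unfavourable effects (Section 3.4), so it has the same gap. A statistical analysis plan cannot repair this, because the information would not have been collected.

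**Working it through.** No figure in the plan is in dispute. The check is a field-by-field comparison, followed by a short piece of algebra on the direction of the error.

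**Step 1. Section 6 Referral categories against the two forms.**

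| Section 6 category | Index form (Annex 2) | 3/9-month form (Annex 3) |
|---|---|---|
| None | box | box |
| Hospital or emergency | box | no box; only an admission is visible, in the hospitalisation block |
| Cardiologist | box with delay categories | box and number of visits, no delay |
| New consultation | box | total count of later consultations, setting not asked |
| Other | box, free text | other specialist, free text |

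Every category except hospital/emergency has some counterpart at follow-up. For that one, the part that ends in admission can be seen elsewhere; the part that ends in discharge cannot.

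**Step 2. Where could a discharged emergency referral be entered?** Annex 3 has five blocks.

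- Later consultations: it could be counted here, but would be merged with ordinary return visits to the GP.
- Investigations after inclusion: tests done in the emergency setting could be counted, but not the referral.
- Specialist referral: a GP might write it in as another specialist. Nothing on the form asks for this, and practice would vary between GPs.
- Hospitalisation: the item asks for days, and the form does not say how to treat a same-day discharge.
- Retained diagnosis: coronary disease yes or no; the route to the diagnosis is not asked.

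The event has possible homes but no dedicated one.

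**Step 3. Effect on the between-arm difference.** For arm *i* (1 = score, 0 = usual care), let *a_i* be the mean number per patient of emergency referrals at the index visit. Let *b_i* be the mean number after it that do not end in admission. Let *r* be the share of these later referrals that are nevertheless written into the specialist block, assumed equal in both arms.

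- True difference: (*a_1* − *a_0*) + (*b_1* − *b_0*)
- Recorded difference: (*a_1* − *a_0*) + *r*(*b_1* − *b_0*)
- Recorded minus true: −(1 − *r*)(*b_1* − *b_0*)

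If the score only postpones a quantity *d* of referrals, then *a_1* − *a_0* = −*d* and *b_1* − *b_0* = +*d*. The true difference is 0 and the recorded difference is −(1 − *r*)*d*, an apparent saving. If later referrals are equally frequent in both arms, the error is 0 with a common *r*. The bias thus depends on a shift in timing and on incomplete entry. The protocol gives no value for *b*, *d* or *r*.

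**The case against.** **Section 6 may be a pooled list.** Only the patient-outcome row carries a time label, and the cardiologist delay categories are also absent from Annex 3, so the follow-up form may never have been meant to repeat every sub-item. This is possible. But the text of Section 6 names both time points for the impact criteria, and Annex 3 does ask about referral again, so the reading is weak.

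**The form is not blind to serious consequences.** This stands. Admission, its duration and the retained coronary diagnosis are all collected, tests done after inclusion are counted whatever the setting, and free text could hold an emergency referral. The accurate statement is that no dedicated field exists; to say the event can never be identified would go too far.

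**A reader might infer that the plan promised to capture every emergency attendance, including a reassured patient who goes on their own initiative and is sent home.** The documents do not support that. Section 3.2 speaks of referrals run by GPs, and Section 6 lists the item as a referral destination. Leaving self-presented visits off Annex 3 contradicts nothing in the protocol, though recording them would be informative.

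**A reader might also want to attach a number of lost events, or the power to detect a rise.** Neither can be supported. Section 10.1 gives earlier rates for tests, specialist referral and hospitalisation, but none for emergency visits without admission.

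**Conclusion.** The mismatch holds. Section 6 assigns a hospital/emergency referral category to follow-up, and the form used at 3 and 9 months does not carry it. What is affected is a GP referral to an emergency setting, after the index visit, that does not end in admission. It cannot be counted reliably in the Referral comparisons of Section 10.2 e and f. A referral that the score merely postpones may then be read as one it avoided.

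The form is the same for all 15,000 planned patients in both arms, but the size of any bias is unknown. It is zero if later emergency referrals are equally frequent in both arms and equally likely to be written in elsewhere. It favours the score if use of the score shifts referrals to a later date. The finding concerns the Referral endpoint and the information available at the 3-month look. It does not show that missed coronary disease or admissions would go unrecorded.

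**What to change.** Before enrolment, add one line to Annex 3 for hospital or emergency attendance for chest pain after inclusion: yes/no, number, referred by the GP or self-presented, admitted yes/no. Count the GP-referred visits under Referral in Section 10.2 e and f. Self-presented visits can be tabulated by arm as a descriptive safety signal at 3 months and at the end of follow-up. They need not be added to the patient-outcome row, which Section 6 limits to hospitalisation and coronary disease.

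Stating in Section 6 that this category is recorded at the index visit only would remove the contradiction, but would leave postponed referrals out of the comparison; the added line is the better choice.

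The cost is one line on an existing form, with no extra visits or contacts. It must be done before the first follow-up data are collected.

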### **Hospitalisations en lien avec la douleur thoracique durant la période de suivi :**

oui  / non

*Si oui*, durée : \_\_\_\_ jour(s)

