### 3.1 Overall description

This trial aims to assess implementation of a new cardiovascular CPR in primary health care. It is built as a prospective cohort study of primary care patients with chest pain. The cluster randomized trial design allows us to randomize GP's offices in two groups, one using the CPR in daily practice and the other working without, according to usual care practice. Thus, randomization and intervention are targeted at the level of GP's offices. Patient's outcome however is measured at the individual's level thanks to a case report form (CRF). Use of the CPR is measured directly by a few questions intended for GPs.

GPs selected to use the cardiovascular CPR will get intensive training to make as sure as possible that they use it in an equivalent way (see Annex 1 for description of GPs training). GPs of the usual practice group should not be aware of the CPR and will not get any information about it. In both groups, GPs will have to fill in a CRF for each patient complaining of chest pain.

Follow-up ends nine months after patient's index visit. An intermediate analysis is planned at three months. Members of research staff are designed to make sure that case report forms are complete for each patient and will get in touch with every agreeing patient at three months (intermediate analysis). GPs will assure the follow up until nine months (end of follow up) either by telephonic interviews or usual consultation. The research staff will control the follow up and remember GPs if necessary.

Independent physicians will review a defined randomized number of cases. They will control patient's condition at the end of the follow-up, validate the correct management of patients and verify the validity of the initial diagnosis of cardiogenic chest pain.

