### 3.5 Data collected in the CRF

A case report form (CRF) has to be filled in by all the GPs for each patient included to define patient's characteristics, current pain, personal history of cardiovascular disease and risk factors. It will also provide investigators with information regarding complementary investigations, referrals or hospitalizations for each patient at the time of index visit.

GPs of the intervention group will be asked to calculate the risk of cardiogenic chest pain for each patient with the CPR. The CRF also includes questions directly addressed to GPs to appreciate use, satisfaction and acceptability of the CPR.

GPs who belong to the usual care group will have to evaluate the risk of cardiogenic chest pain according to their clinical judgement only.

As all the items of the CPR are part of usual practice (patient's history and physical examination) investigators will be able to calculate patients' risk of cardiogenic chest pain a posteriori in the usual care group with the data collected in the CRF.

[figure not shown]
(See Annex 2 for complete CRF)

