## Suivi à 3 et 9 mois

Questionnaire rempli par : infirmière de recherche (analyse intermédiaire à **3 mois**)   
 médecin (terme du suivi à **9 mois**)

No patient :	No médecin :	Date :
--------------	--------------	--------

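### Hospitalisation is an unrestricted endpoint in sections 3.2 and 6, but the follow-up form records only admissions judged linked to the chest pain

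*Protocol*

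**What the plan says.** Protocol section 3.2 lists the patient outcome as "Hospitalizations, severe CHD at 9 months among patients included". Section 6 lists "Hospitalisation(s) during follow-up" under outcome at 9 months. Neither limits admissions by cause.

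The Annex 3 follow-up form (Suivi à 3 et 9 mois) is the only instrument that collects admissions after the index visit. Its item reads "Hospitalisations en lien avec la douleur thoracique durant la période de suivi", answered yes or no, with a length of stay in days if yes. It has no space for other admissions, or for the date, reason or number of those reported.

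The same form serves both time points and names who completes it: "infirmière de recherche (analyse intermédiaire à" 3 months and "médecin (terme du suivi à" 9 months. Section 3.1 confirms that "GPs will assure the follow up until nine months (end of follow up) either by telephonic interviews or usual consultation". On knowledge of the intervention, section 3.5 says "GPs of the intervention group will be asked to calculate the risk of cardiogenic chest pain for each patient with the CPR", and section 3.1 says "GPs of the usual practice group should not be aware of the CPR".

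**The concern.** The second objective is to show that tests can be spared without making patients' management or outcome worse. Hospitalisation and CHD at 9 months are the only two patient outcomes that can support the second half of that claim.

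The harm to look for is a false rule-out: pain judged non-cardiac, followed by a coronary event. The form filters admissions by whether they are linked to the index pain. A GP who concluded that the pain came from the chest wall can, in good faith, regard a coronary admission at month 4 as a separate matter and answer no. The endpoint would then miss the event it is most needed for.

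The filter is applied by the clinician whose earlier judgement is under test. In one arm that judgement was informed by a score and in the other it was not, so the threshold for calling an admission linked may differ between arms. The 3-month analysis uses the same item, so the check for unfavourable effects in sections 3.4 and 8.2 has the same gap.

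**Working it through.** **1. Definition against instrument**

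| Place | Restriction on investigations | Restriction on hospitalisation |
|---|---|---|
| Section 3.2 | Those run to manage the chest pain | None |
| Section 6 | Those for chest pain | None |
| Annex 3 | Those for the chest pain | Only those linked to the chest pain |

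Sections 3.2 and 6 state a chest-pain limit for investigations and none for hospitalisation. The form adds one and gives no rule for judging the link.

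**2. Who judges the link**

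- 3 months: research nurse, by telephone, with patients who agreed (sections 3.1 and 7.2).
- 9 months: treating GP (section 3.1, Annex 3). In the CPR arm this GP calculated the score. In the usual-care arm the GP is not told of the CPR.

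**3. Other routes by which a missed admission could surface**

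- The CHD item in Annex 3 asks for the diagnosis retained for the chest pain, so it is tied to the index pain in the same way.
- Independent review covers a random 20% of cases (section 9.1). No section describes classification of admissions without knowledge of arm.
- The index CRF records referral to hospital or emergency at that visit only.

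**4. How many patients are exposed**

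Inputs: 150 GPs per arm with 50 patients each (section 10.1); CHD in 12% of primary care chest pain (section 1.1); Swiss score sensitivity 97.6% in derivation and 85.6% in validation (sections 1.2 and 5).

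- Planned size: 2 × 150 × 50 = 15,000, as stated; 7,500 per arm.
- CHD patients in the CPR arm: 0.12 × 7,500 = 900.
- Scored low risk = 900 × (1 − sensitivity): 900 × 0.024 = 21.6, about 22; 900 × 0.144 = 129.6, about 130.
- As a share of the arm: 22/7,500 = 0.3% and 130/7,500 = 1.7%.

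This is the pool of patients at issue, not a count of lost events. Not all would be admitted, not all admissions would be answered no, and usual-care GPs also misjudge some CHD patients.

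**5. What uncounted events would do to the comparison (illustration only)**

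Assumptions: two-sided alpha 0.05; control rate p0 = 53/672 = 7.9% (section 10.1); C = 150 clusters per arm; m = 50; coefficient of variation k = 0.2 (section 10.1).

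Variance of the difference: v = [p0(1−p0)/m + p1(1−p1)/m + k²(p0² + p1²)]/(C−1). Power = Φ(|p1−p0|/√v − 1.96).

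Take a true excess of 1.0 percentage point in the CPR arm, which is 75 patients and so possible only towards the upper end of the pool in step 4.

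- All counted: p1 = 0.0889, √v = 0.00494, power = Φ(2.02 − 1.96) = 53%.
- A quarter of the excess answered no: 33%.
- Half of the excess answered no: p1 = 0.0839, √v = 0.00486, power = Φ(1.03 − 1.96) = 18%.

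The uncounted share is assumed; the documents give nothing from which to estimate it.

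**The case against.** The best defence is that sections 3.2 and 6 are loosely worded and that Annex 3, which ties its clinical items to the chest pain, is the working definition. This stands in part. Neither section says any or all-cause, so a reader who infers two explicitly opposed definitions goes beyond the text. The mismatch remains, because the endpoint as listed is not what the form collects.

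Safeguards exist. For agreeing patients a nurse covers the first 3 months, a GP who learns of a coronary admission must still answer the CHD item, and one case in five is reviewed. Each is partial: the nurse asks the same restricted question, the CHD item concerns the index pain, and four cases in five go unreviewed.

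Three stronger readings are tempting, and the documents do not support them.

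- *The filter biases the result in favour of the score.* This is plausible but not shown. Usual-care GPs also record an initial CHD judgement with a degree of certainty, so GPs in both arms have a view to defend.
- *The loss can be sized.* If CPR-arm GPs called 10% to 20% more admissions unrelated, 60 to 120 of 600 (8% of 7,500) would vanish. That rate has no source. It also fits the mechanism badly: 60 to 120 exceeds the pool of 22, and would need 46% to 93% of the pool of 130 (60/129.6 and 120/129.6). The 8% is a 12-month figure, not stated to be all-cause or chest-pain-related.
- *Missed admissions are lost for good.* GPs keep a list linking codes to names and phone numbers (section 7.2), and section 10.3 makes contact with GP or patient the first step for missing data. Recovery would be laborious, since the research team's phone numbers are deleted after the 3-month analysis, but not impossible.

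**Conclusion.** The point holds as a mismatch between endpoint and instrument. Hospitalisation is listed without limit by cause, while the form counts only admissions that someone links to the chest pain. At 9 months that person is the treating GP, who in the CPR arm calculated the score. A coronary admission after pain judged non-cardiac can go uncounted, and attribution may differ between arms.

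Neither the size nor the direction of a resulting bias can be derived. What can be said is that about 22 to 130 CHD patients in the CPR arm would score low risk, given 12% prevalence, 7,500 patients and the two stated sensitivities. The conclusion rests on the wording and not on the power illustration. It matters because so few outcomes carry the safety half of the objective, and it should be settled before the form is used.

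**What to change.** - Reword the Annex 3 item to record every hospital admission since the index visit, whatever the reason, with date and discharge diagnosis, and with room for more than one.
- Align sections 3.2 and 6 with the form, stating that all admissions are collected and which are counted.
- Derive cardiac or chest-pain-related admission from the recorded diagnosis by one written rule, applied to both arms without knowledge of arm.
- Report that derived outcome together with all-cause admission. All-cause alone is not enough, because unrelated admissions can dilute a real excess towards no difference; related admissions alone depend on the classification.

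The cost is a few more lines on the form and some extra coding of diagnoses. The planned number of GPs and patients and the clinical care of patients do not change.

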### **Diagnostic retenu pour la douleur thoracique :**

Maladie coronarienne : oui  / non

Degré de certitude : faible 0 - 1 - 2 - 3 - 4 fort
